Another interesting aspect in relation to antimalarial is that the mechanism of its beneficial effect has not yet been fully clarified, but it is believed to be correlated with the blockade of toll-like receptors (TLR7-9) and inhibition of alpha interferon production, which plays a crucial role in the pathogenesis of SLE. In fact, an *in vitro* study observed that the use of hydroxychloroquine inhibits the production of interferon-alpha and TNF by plasmacytoid dendritic cells of patients with SLE and, apparently, this inhibition is more effective for TLR-9 than for TLR-7 (Sacre et al., 2012). However, there is still a need to determine the possible correlation between the level of antimalarial and the degree of inhibition of the two different receptors.

Objectives primary:

- Monitoring of HCQ blood levels: possible relevance on disease activity in JSLE and renal adult SLE to inclusion and 6 months following inclusion.

Secondary:

- Evaluate the predictive value of HCQ levels for JSLE disease activity and renal disease activity in adult SLE within 6 months of inclusion.

- To verify the possible association between blood levels of HCQ with adherence to treatment assessed by a specific questionnaire.

- Evaluate the correlation between blood and salivary levels of HCQ in a subgroup of patients with SLE and JSLE and their possible association with therapeutic response and safety.

- Check whether the production of interferon-alpha and TNF by plasmacytoid dendritic cells correlates with blood HCQ levels.

NUMBER OF INDIVIDUALS

Total patients required for the study = 309, being: SLE (n= 206), SLEJ (n= 103).

STUDY DESIGN

Initially, a cross-sectional study will be conducted with patients using HCQ at a dose of 5-6.5 mg/kg/day (maximum of 400 mg/day) for at least 6 months (Clark et al., 1993). At the entrance, peripheral blood samples will be taken to determine HCQ levels and patients will be evaluated for the activity of the underlying disease in a "blind" way to HCQ concentrations.

The following indices will be used to assess disease activity every 3 months:

- SLE and SLEJ: Systemic Lupus Erythematosus Disease Activity Index (SLEDAI-2K) (Gladman et al., 2002) and active disease randomly defined as SLEDAI-2K \geq 6.

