Currently, it is recommended that all patients with SLE should be treated with antimalarials unless specific contraindications (Wallace et al., 2012; van Vollenhoven et al., 2014). Its use is justified because of the demonstrated effectiveness in the treatment of the disease (Ruiz-Irastorza et al., 2010), with a decrease in inflammatory episodes (flares) (Clark et al., 1993). Furthermore, it was demonstrated that HCQ withdrawal increases the risk of disease reactivation (The Canadian Hydroxychloroquine Study Group, 1991; Tsakonas et al., 1998). There is a modulating effect on the immune response with its use, promoting a change in the production of pro-inflammatory cytokines, and these effects are probably mediated mainly by inhibition of receptor-7 and -9 Toll-like (Wallace et al., 2012). The most commonly used dosage is 400 mg/day of HCQ. It is also relevant in the context of treatment that antimalarials have a long half-life of approximately 40 days and there is a delay to reach plasma concentration with a therapeutic effect expected only after 3 months or more of treatment (Rodriguez-Caruncho et al., 2014). Monitoring the level of this medication, which was established as at least 1000 ng/mL, would certainly be very useful for determining whether a higher attack dose would allow this therapeutic effect to be achieved more quickly. Lower blood concentrations of HCQ (< 1,000 ng/mL) determined by HPLC MS/MS are associated with higher inflammatory activity of SLE (Costedoat-Chalumeau et al., 2006). Adequate serum levels of the metabolites of this drug are related to a better efficacy in the treatment of the cutaneous form of lupus (Francès et al., 2012), but even using the same daily dose of the drug, there is a great individual variability among patients (Munster et al., 2002). Therefore, in rheumatoid arthritis, it

has been suggested that an attack dose in the first weeks of treatment is related to an increase in response in this period (Emery, 1999; Furst et al., 1999). There are no studies in SLE that assess how long after the start of treatment is necessary to achieve adequate HCQ blood level, nor whether a higher initial dose (attack) could anticipate these levels in order to provide an earlier clinical/laboratory response.

Objectives Primary objective:

- Compare the time required to reach the level of 1000 ng/mL of HCQ in patients with SLE, using standard dose vs. attack dose.

Secondary objective:

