- Evaluate the clinical/laboratory response and adverse events in both groups.
- Verify a possible correlation of HCQ concentrations in blood and saliva with interferon-alpha and TNF production levels by plasmacytoid dendritic cells and disease activity parameters.
- Correlate blood and salivary levels of HCQ and its metabolites in Patients with SLE with adherence to this treatment.

NUMBER OF INDIVIDUALS

Total patients needed for the study = 96 (SLE).

STUDY DESIGN

Prospective randomized study controlled for a period of six months of patients with SLE who will start the use of HCQ.

Patients will be randomized randomly into two groups: traditional group - without increasing the daily dose (HCQ 400 mg/day); attack dose group - with increased daily dose (HCQ 800 mg/day for 6 months). Patients will be evaluated for the activity of the underlying disease in a "blind" way. HCQ concentrations will be assessed at the entrance and at the end of the study.

The groups will be compared for episodes of disease activity (clinical and laboratory parameters), inflammatory cytokines, and expression of TLR-7 and TLR-9 receptors.

Blood concentrations of HCQ and metabolites will be determined in both groups by HPLC (Munster et al., 2002).

The following indexes will be used to assess disease activity:

- SLE: SLEDAI-2K (Gladman et al., 2002) and active disease randomly defined as SLEDAI-2K \geq 6.

- Renal activity: BP, urine type I, protein and creatinine in an isolated urine sample, serum creatinine, C3, C4, anti-dsDNA, according to the ACR Guidelines (Hahn et al., 2012).

Adherence will be assessed by the MASRI questionnaire applied by a pharmacist not directly involved in patient care (Koneru et al., 2007).

The following clinical, laboratory and treatment data will be evaluated in the groups (traditional dose and attack dose): age, sex, race, weight, height, BMI, ideal weight; disease time, time of HCQ use, adherence to treatment; smoking; use and dose of prednisone, methotrexate, azathioprine, mycophenolate mofetil, cyclophosphamide, non-hormonal anti-inflammatory drugs; urinary protein/creatinine ratio; serum creatinine; HCQ blood concentrations by HPLC MS/MS; general- gastrointestinal and cutaneous adverse events.

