The sample size was calculated considering that the faster the 1000 ng/mL blood level is reached, the greater the improvement in lupus activity and the lower the recurrence rate in the groups is observed, 6 months after the onset of HCQ treatment. In the study by Tett et al., 2000, in patients with AR, in the group that started HCQ at a dose of 400 mg/d, the mean seric level was 870.3 ± 329.3 ng/mL, that is, about 34% of patients reached > 1000 ng/mL blood level after 6 months. It is estimated that more than 20% of patients will reach this value with twice the attack dose, we calculate (based on: 95% confidence interval, error α 5%; power of 80%) expected frequency of patients with 1000 ng/mL > level after 6 months in the 400 mg/d group: 34%; expected frequency of patients with 1000 ng/mL > level after 6 months in the 800 mg/d group: 55 %; losses: 10%; n = 96.

STATISTICAL PLAN

The comparison of the time required to reach the level of 1000 ng/mL of HCQ in patients with SLE and JSLE, using survival curve by log-rank test. Categorical variables will be evaluated by Fisher's exact or chi-square test and quantitative variables by Student and Mann-Whitney *t* tests, when applicable.

Project 2: THALIDOMIDE

EVALUATION OF THE TREATMENT OF CUTANEOUS LUPUS ERYTHEMATOSUS WITH THALIDOMIDE: CLINICAL, LABORATORY AND HISTOLOGICAL FACTORS ASSOCIATED WITH CLINIC RESPONSE AND ADVERSE EFFECTS

Diseases

Systemic lupus erythematosus with cutaneous involvement (LEC).

Justification

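### Subproject 1C sets out to compare time to 1000 ng/mL by log-rank, but samples HCQ only at entry and month 6, so it can compare only month-6 proportions

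*Combined protocol and SAP*

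**What the plan says.** All references are to subproject 1C of the combined protocol and SAP unless noted.

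- **Primary objective:** "Compare the time required to reach the level of 1000 ng/mL of HCQ in patients with SLE, using standard dose vs. attack dose".
- **Statistical plan:** this time is compared "using survival curve by log-rank test".
- **Study design, duration:** "Prospective randomized study controlled for a period of six months of patients with SLE who will start the use of HCQ".
- **Study design, sampling:** "HCQ concentrations will be assessed at the entrance and at the end of the study".
- **Sample size:** the inputs are the expected percentages above 1000 ng/mL after six months, 34% on 400 mg/day and, "in the 800 mg/d group: 55 %; losses: 10%; n = 96". Alpha is 5% and power 80%. No hazard ratio or number of events is given.
- **Number of individuals:** "Total patients needed for the study = 96 (SLE").

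Nothing else in the document supplies an intermediate HCQ sample for 1C. The list of data to be collected names HCQ concentrations without times. The cross-reference to subproject 1A stands under Relevant methods, which in 1A describes assays. The three-monthly schedule in 1A is for something else: "The following indices will be used to assess disease activity every 3 months". The 6- and 12-month HCQ samples belong to subproject 1B.

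**The concern.** A time-to-threshold comparison needs to know, at least roughly, when each patient crossed the threshold. With one sample after entry, a patient above 1000 ng/mL at month 6 may have crossed at any time in the six months, and the data cannot separate an early crossing from a late one. A patient who crossed and has fallen back below the level by month 6 counts as never having reached it.

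The 1C justification asks how long it takes to reach an adequate level and whether a higher starting dose brings that forward. A positive log-rank result from this schedule could be reported as faster attainment although no data on speed exist.

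Once the endpoint is recognised as a month-6 proportion, the sample size can be checked against it. The stated total then does not appear to give the stated power.

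**Working it through.** **1. The plan's own sample size.** Inputs from the 1C Sample size section: p1 = 0.34, p2 = 0.55, alpha 0.05, power 0.80, losses 10%. Sidedness is not stated; I take two-sided.

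Pooled formula, with mean proportion 0.445:

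n = [1.96·√(2·0.445·0.555) + 0.8416·√(0.34·0.66 + 0.55·0.45)]² / (0.55 − 0.34)²
= (1.3775 + 0.5781)² / 0.0441 = 86.7, so 87 per arm.

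With losses: 86.7/0.9 = 96.4; 87/0.9 = 96.7; 87 × 1.1 = 95.7. So 96 is reproduced as a **per-arm** figure, giving a total of 192 to 194. It is not reproduced as a total. One-sided, unpooled and continuity-corrected versions give 75 to 108 per arm after losses, so none gives 96 in all.

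**2. Power if 96 is the total** (1:1 allocation assumed; the ratio is not stated). Power = Φ[(0.21·√n − 1.3775)/0.6870].

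| Per arm | Chi-square power | Fisher's exact power | Detectable against 34% at 80% power (chi-square) |
|---|---|---|---|
| 48 (no losses) | 54% | 47% | 62.2% |
| 43 (10% losses) | 50% | 41% | 63.8% |

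**3. The log-rank with one event time.** Take 43 per arm (N = 86), with 15 standard-dose and 24 attack-dose patients above the level, 39 in all.

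- Expected attack-dose events: 39/2 = 19.5.
- Log-rank variance: 39 × ¼ × (86 − 39)/85 = 5.391. Statistic: (24 − 19.5)²/5.391 = 3.756 (p = 0.053).
- Pearson: the same with 86 in place of 85, giving 3.800 (p = 0.051).
- Ratio: 85/86 = (N − 1)/N.

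**4. The same 39 patients, had monthly samples shown when they crossed.**

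*Attack dose at month 2, standard dose at month 6.*
- Month 2: 43 and 43 at risk, 24 events; expected attack-dose events 12, variance 24 × ¼ × 62/85 = 4.376.
- Month 6: 19 attack and 43 standard at risk, 15 events; expected 15 × 19/62 = 4.597, variance 15 × (19/62) × (43/62) × 47/61 = 2.456.
- Statistic: (24 − 16.597)²/6.833 = 8.02.

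*Standard dose at month 2, attack dose at month 6.*
- Month 2: 15 events; expected 7.5, variance 15 × ¼ × 71/85 = 3.132.
- Month 6: 43 attack and 28 standard at risk, 24 events; expected 24 × 43/71 = 14.535, variance 24 × (43/71) × (28/71) × 47/70 = 3.849.
- Statistic: (24 − 22.035)²/6.981 = 0.55.

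The stated schedule returns 3.76 in both cases.

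**5. What month 6 measures.** The 1C justification gives a half-life of about 40 days. Six months is about 4.5 half-lives, so under first-order accumulation about 96% of steady state has been reached. The final sample mainly shows the level attained.

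**6. Rough size if the speed question is kept.** Assume proportional hazards and near-continuous sampling. HR = ln 0.45/ln 0.66 = 1.92; events = 4 × (1.96 + 0.84)²/(ln 1.92)² = 74; N = 74/0.445 = 167; 167/0.9 = 186 in total.

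**The case against.** **The test is not invalid, and little power is lost.** This is true. The log-rank and chi-square statistics differ only by 85/86 here. In a simulation with exponential crossing times, month-6-only and monthly sampling gave nearly equal power: 49% and 51% with 43 per arm, 81% for both with 86 per arm. The damage is to what can be concluded.

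**A higher month-6 proportion does say something about timing.** It shows that more patients are above the level at that point, and if accumulation were similar in both arms it would suggest earlier crossing. That rests on an assumption, not on observed times. The two cases in step 4 are extremes chosen to show the blindness, not a plausible range.

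**The exact equivalence has conditions.** Patients must be below 1000 ng/mL at entry, which fits patients starting HCQ, and must be sampled at one nominal date. An early leaver's final sample would add another date, but still not a crossing time.

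**The sample size is a separate matter.** The ambiguity over 96 exists under any endpoint. It belongs in the same edit because the sample-size inputs are those of the month-6 proportion.

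**The stated purpose is speed, so adding samples serves it better.** This is a fair argument for the second remedy below, and the choice is the sponsor's. If 96 was meant per arm, the resulting 192 already exceeds the idealised 186.

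**Conclusion.** The concern holds. As written, the primary objective of 1C cannot be answered: the scheduled samples reduce the log-rank to a comparison of month-6 proportions. This conclusion needs only entry levels below the threshold and a common final sampling time.

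The stated total of 96 does not deliver 80% power for 34% against 55%. It gives about 54%, or 50% after 10% losses, assuming 1:1 allocation and a two-sided 5% test. As a per-arm figure, 96 agrees with the inputs. Intermediate sampling may have been intended, but it is not written. The point should be settled before any data are analysed.

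**What to change.** **Preferred: match the endpoint to the data.**
- Make the primary endpoint the proportion of patients above 1000 ng/mL at six months.
- Name one test in advance. The plan leaves it open, listing Fisher's "exact or chi-square test and quantitative variables by Student" and other tests for quantitative variables; chi-square agrees with the sample-size calculation.
- Remove the log-rank test and the claim about time.
- State whether 96 is per arm or total. If per arm, correct the total to about 192 to 194. If total, state the real power (about 50% to 54%) or the detectable difference (34% against about 62% to 64%).
- Reconcile the population: the statistical plan names SLE and JSLE, while the objective and the number of individuals name SLE only.

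The endpoint and test change costs only wording and gives up the speed claim. Settling n is also wording if 96 was per arm; otherwise the choice is between roughly doubling recruitment and openly accepting lower power.

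**Alternative: keep the speed question.** Schedule intermediate HCQ samples, use an interval-censored or discrete-time comparison, and redo the sample size. This costs extra blood draws and assays, and possibly extra visits, since 1C states no intermediate visit. Step 6 gives about 186 patients including losses as an idealised starting point; sparse sampling would need somewhat more.

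### Subproject 1C: time to 1000 ng/mL is tested by log-rank, but with HCQ measured only at entry and month 6 the test reduces to a comparison of two month-6 proportions

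*Combined protocol and SAP*

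**What the plan says.** All references are to Subproject 1C of the combined protocol and SAP.

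- **Primary objective:** "Compare the time required to reach the level of 1000 ng/mL of HCQ in patients with SLE, using standard dose vs. attack dose".
- **Statistical Plan:** that comparison is made "using survival curve by log-rank test". Fisher's exact or chi-square tests are listed for categorical variables generally.
- **Study Design:** a six-month randomised study of "patients with SLE who will start the use of HCQ". One group takes 400 mg/day and the other 800 mg/day for the full six months. On sampling: "HCQ concentrations will be assessed at the entrance and at the end of the study".
- **Justification:** the half-life is given as about 40 days, and "there is a delay to reach plasma concentration with a therapeutic effect expected only after 3 months or more of treatment".
- **Sample Size:** the inputs are two month-6 proportions, "expected frequency of patients with 1000 ng/mL > level after 6 months in the 400 mg/d group: 34" per cent and "expected frequency of patients with 1000 ng/mL > level after 6 months in the 800 mg/d group: 55" per cent, with 5% alpha, 80% power, 10% losses and n = 96. Number of Individuals gives 96 as the total.

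Nothing else in 1C adds an HCQ sampling time. The HPLC sentence and the list of data items carry no dates. The cross-reference to Subproject 1A is under Relevant Methods, and 1A's three-monthly schedule is for disease activity indices, not drug levels. Where the programme wants serial drug levels it says so: the thalidomide project lists them at 30 days and at 3, 6, 9 and 12 months.

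**The concern.** A time-to-event comparison needs to know roughly when each event happened. Patients here are starting HCQ, so the entry sample cannot show a crossing and month 6 is the only sample that can. Someone who passed 1000 ng/mL in week 6 and someone who passed it in week 25 receive the same event time.

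This affects the stated reason for 1C, which is that no SLE study shows how long an adequate level takes or whether a higher starting dose shortens that time. A significant log-rank test on a survival curve would naturally be reported as a faster rise, and the data could not support that. Samples not taken during the six months cannot be recovered afterwards. The sample size is also built on month-6 proportions, so the objective and the sizing describe different endpoints.

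**Working it through.** **1. What the log-rank test becomes.** Let N patients have a month-6 sample, n₁ and n₂ per group, with a and b above 1000 ng/mL and d = a + b. With one event time:

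- E = d·n₁/N
- V = d·n₁·n₂·(N−d) / [N²(N−1)]
- log-rank χ² = (a−E)²/V = [(N−1)/N] × Pearson χ²

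Take 48 per group with 16 and 26 above the level, close to the planned proportions:

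- E = 42×48/96 = 21; V = 42×48×48×54/(96²×95) = 5.968; log-rank = 25/5.968 = 4.189
- Pearson = 96×(16×22 − 26×32)²/(48×48×42×54) = 4.233
- Ratio 0.9896 = 95/96; p = 0.041 v 0.040

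The date of crossing within the six months appears nowhere in the statistic.

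**2. What this costs if speed differs.** A simulation under assumed conditions: 48 per group, 80% of both groups cross by month 6, median crossing day 120 v 50. The log-rank test rejects in about 6% of trials with month-6 sampling only, which is close to the alpha level, and in about 86% with monthly sampling.

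**3. Where month 6 falls.** With the plan's 40-day half-life, 1 − 2^(−180/40) = 0.956, so the month-6 sample is at about 96% of steady state. It compares two sustained doses.

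**4. The plan's sample size.** The 34% comes from a cited mean of 870.3 ± 329.3 ng/mL. Under normality P(>1000) = 1 − Φ(129.7/329.3) = 34.7%, so it reproduces. For 34% v 55% (two-sided 5%, 80% power, 1:1 allocation assumed, mean proportion 0.445):

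- n = [1.96√(2×0.445×0.555) + 0.8416√(0.34×0.66 + 0.55×0.45)]² / 0.21² = 86.7, so 87 per group
- With 10% losses: 87×1.1 = 95.7 (96), or 87/0.9 = 96.7 (97), per group

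So 96 reproduces as a number per group, not as the stated total. With 96 in total, power is Φ[(0.21√48 − 1.3775)/0.687] = 54%. With 43 evaluable per group it is 50%. A one-sided test would still need 154 in total after losses.

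**5. What a week-12 level could offer.** The plan gives no level at 800 mg/day, so a rise must be assumed. Take week-12 level = month-6 level × (1 − 2^(−84/40))/0.956 = 0.802 × month-6 level, a constant coefficient of variation and 43 per group. The SLE means are those in Subproject 1A's sample size: 694 ± 448 (active) and 1079 ± 526 (inactive).

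| Source of the 400 mg/day level | Shape | Assumed rise | Week 12, 400 v 800 mg/day | Power |
|---|---|---|---|---|
| 1C, 870.3 ± 329.3 | normal | 1.5 | 13% v 55% | 99% |
| 1A inactive | normal | 1.5 | 37% v 68% | 82% |
| 1A active | normal | 1.5 | 11% v 38% | 85% |
| 1A active | lognormal | 1.5 | 10% v 27% | 55% |
| 1C, 870.3 ± 329.3 | normal | 1.206 | 13% v 31% | 54% |
| 1C, 870.3 ± 329.3 | lognormal | 1.206 | 12% v 26% | 36% |

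The factor 1.206 is the rise that yields the plan's own 55% at month 6 under normal levels: 1000/(870.3 − 0.1257×329.3). In the last row the corresponding month-6 power is 45%.

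**The case against.** Three points on the other side are fair.

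First, a reader might infer that the planned test says nothing at all about speed. That goes too far. The share above 1000 ng/mL at month 6 is one point on the time-to-level curve. The supportable statement is that the samples cannot show when, within the six months, the level was reached.

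Second, a valid randomised comparison survives. The trial is already sized on month-6 proportions, and the plan already names tests for categorical variables. Much of the repair is therefore relabelling. This stands, and it is why the repair is cheap; it does not make the present objective answerable.

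Third, a reader might infer that early samples would rescue the speed question with no added patients, or that week 12 would be no worse than month 6. Some favourable cases suggest this, but it depends on the assumed rise and on normally distributed levels. The active-SLE figures (694 ± 448) put about 6% of a normal distribution below zero. With lognormal levels the 1.5-fold case in active SLE has 55% power, and in the 1.206-fold lognormal case week 12 is worse than month 6 (36% v 45%). The documents do not support either inference.

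Whether 96 is a total or a number per group is a separate matter. If it was meant per group, the power shortfall disappears and the timing problem remains.

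**Conclusion.** The point holds and should be fixed before the analysis is relied on. The primary objective, the test and the sampling schedule in 1C do not fit together: the log-rank test is the month-6 chi-square scaled by (N−1)/N. A positive result supports only a higher proportion above 1000 ng/mL at month 6 on sustained 800 mg/day, not a shorter time to that level. This follows from the documents and algebra, without any pharmacokinetic assumption.

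For the endpoint that remains, the stated total of 96 gives about 54% power under 34% v 55%, or 50% after 10% losses. That rests on equal allocation and a two-sided 5% test, neither of which the plan states. The 55% is itself the plan's assumption. The week-12 figures are illustrations and carry no weight in this conclusion.

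**What to change.** **Option A (wording only).**

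- Make the proportion above 1000 ng/mL at month 6 the primary endpoint, with a two-proportion test.
- Remove the log-rank test and any conclusion about time to level, and describe the result as a comparison of two sustained doses.
- State whether 96 is the total or per group. If it is the total, report power of about 54% (50% after losses) for 34% v 55%. Holding 80% power would take 97 per group, 194 in total.

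**Option B (if speed stays the question).**

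- Add HCQ levels before month 6, for example at weeks 8 and 12.
- Analyse time by visit or as interval-censored data over those visits and month 6.
- The cost is two more samples per patient, 2 × 96 = 192 assays at 96 patients, plus the visits to collect them, since 1C lists no interim visit.
- Justify the sample size from a stated assumption about levels at 800 mg/day, with a range. At 43 per group an assumed 1.5-fold rise gives week-12 power of about 55% to 99%, and the rise implied by the plan's own 55% gives about 36% to 54%.

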- The production of interferon-alpha and TNF-alpha by plasmacytoid dendritic cells will be evaluated in vitro using mononuclear cell preparations isolated from peripheral blood from a random sample of the same number of consecutive patients with active and inactive SLE. The cells will be

stimulated with the TLR-9 agonist, Oligodeoxynucleotides CpG (ODN CpG-A)-2216 and the TLR-7 agonist, imiquimod. The percentage of monocytes, B cells, dendritic cells and natural killers (NK) in the PBMC fraction will be determined by the phenotypic characterization of these cell subpopulations by flow cytometry using monoclonal fluorochrome-conjugated antibodies. Intracellular detection of IFN-alpha and TNF-alpha in plasmacytoid dendritic cells will also be performed by flow cytometry and specific monoclonal antibodies (Sacre et al., 2012).

TARGET POPULATION

Inclusion criteria:

- SLE (ACR criteria) (Hochberg, 1997);
- without using HCQ at a dose of 400 mg/day for at least 6 months.

Exclusion criteria:

- alcoholism;
- renal dialysis;
- concomitant infectious process;
- acute and chronic liver diseases;
- concomitant use of drugs that interact with HCQ (cimetidine, antacids, digoxin, aminoglycosides, penicillin, neostigmine, pyridostigmine).

RELEVANT METHODS

See subproject 1A.

Safety. Monitoring of adverse events and outbreaks of inflammatory activity (flare).

ORIGINALITY WITH IMPACT ON ASSISTANCE

There are no studies in SLE that assess how long after the start of treatment is necessary to achieve adequate HCQ blood and salivary level, nor whether a higher initial dose (attack) could anticipate these levels to provide an earlier clinical/laboratory response without increasing adverse effects.

The expected impact would be that the dosage of HCQ levels would allow to perform a control of the inflammatory activity of the disease earlier and safely.

ADVANCES IN MECHANISMS To compare the inhibitory action of different doses of HCQ in TLRs -7 and -9 and its relevance to the immunomodulatory action of the drug.

SAMPLE SIZE

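### Subproject 1C aims at clinical response in patients who may already be active at entry, but plans no analysis of SLEDAI-2K that uses the entry score

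*Combined protocol and SAP*

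**What the plan says.** All references are to the combined protocol and SAP, Subproject 1C, unless stated.

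- **Aim.** The first secondary objective is: "Evaluate the clinical/laboratory response and adverse events in both groups". Response is not defined. The SAMPLE SIZE text argues that the sooner the target level is reached, "the greater the improvement in lupus activity and the lower the recurrence rate in the groups is observed", so both improvement and recurrence matter to the rationale.
- **Population.** STUDY DESIGN describes a "Prospective randomized study controlled for a period of six months of patients with SLE who will start the use of HCQ". Besides SLE classification, the only inclusion criterion is "without using HCQ at a dose of 400 mg/day for at least 6 months". No inclusion or exclusion criterion mentions SLEDAI-2K, remission or flare. The cell substudy expects both states, since it samples the "same number of consecutive patients with active and inactive SLE".
- **Comparison of activity.** STUDY DESIGN says: "The groups will be compared for episodes of disease activity (clinical and laboratory parameters), inflammatory cytokines". The index is SLEDAI-2K, with "active disease randomly defined as SLEDAI-2K" of 6 or more. Renal activity is listed beside it without a cut-off. The word episode is not defined.
- **Analysis.** STATISTICAL PLAN gives the log-rank test for the time to 1000 ng/mL and, for everything else: "Categorical variables will be evaluated by Fisher's exact or chi-square test and quantitative variables by Student and Mann-Whitney" tests. No change from entry, covariate or stratification is named.
- **Timing.** HCQ levels are taken at entry and at the end. No schedule is given for SLEDAI-2K, and it is absent from the list of clinical data to be evaluated in the groups.

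**The concern.** Response is a change from a starting point, and here patients can start anywhere on the scale. An absolute cut-off applied after entry cannot separate a patient who was active before treatment and is still active from one who became active on treatment. It also gives no credit for a fall that ends at 6 or above.

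Subproject 1B uses nearly the same wording and the same cut-off. Its design takes patients in remission, so a later score of 6 or more can fairly be read as a new outbreak. That reading does not carry over to 1C, which has no remission requirement.

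At stake is what the secondary clinical result of 1C would mean, and how precisely it is estimated. The claimed benefit of the higher initial dose is an earlier clinical and laboratory response, so this is the outcome by which readers would judge whether faster drug levels matter clinically.

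**Working it through.** **No figure to reproduce.** The plan gives no rate, standard deviation or power for SLEDAI-2K in 1C. Its total of 96 patients is derived from the drug-level outcome (34% against 55% above 1000 ng/mL).

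**Step 1: what the cut-off registers.** These are illustrative patients, not data.

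| Entry | Month 6 | Change | Class at month 6 |
|---|---|---|---|
| 10 | 6 | -4 | active |
| 0 | 5 | +5 | not active |
| 10 | 20 | +10 | active |

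The first and third patients fall in the same class although they moved in opposite directions. The second worsened and is not registered.

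**Step 2: precision of the continuous score.** Let r be the within-arm correlation between entry and month-6 scores. It is not in the documents; I assume 0.4 to 0.7. With the entry score as a linear covariate, the residual variance is (1 - r²) times that of the month-6 score alone. The equivalent gain in sample size is 1/(1 - r²) - 1.

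- r = 0.4: 1 - 0.16 = 0.84, so 16% of the variance is removed; 1/0.84 - 1 = 19%.
- r = 0.7: 1 - 0.49 = 0.51, so 49% is removed; 1/0.51 - 1 = 96%.

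These figures compare adjusted with unadjusted analysis of the score. They do not measure the loss from using a cut-off.

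**Step 3: illustration of the cut-off.** This is a simulation of 2,000 trials per scenario. Every input is assumed except the total of 96 and the 10% loss:

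- 43 per arm (96/2 = 48, assuming equal allocation; 48 × 0.9 = 43)
- SD 4, r = 0.5, scores floored at 0
- a mean fall of 2 points in both arms and 2 more in the higher-dose arm
- one reading at month 6
- share active at entry = 1 - Φ((6 - mean)/4)

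| Entry mean | 4 | 6 | 8 | 10 |
|---|---|---|---|---|
| Active at entry | 31% | 50% | 69% | 84% |
| Of those active at month 6, already active at entry | 64% | 76% | 85% | 92% |
| Of those active both times, fell by 4 or more | 15% | 19% | 24% | 28% |
| Power, Fisher on score of 6 or more | 18% | 29% | 37% | 36% |
| Power, Mann-Whitney on month-6 score | 56% | 57% | 61% | 61% |
| Power, month-6 score adjusted for entry | 63% | 68% | 74% | 75% |

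The second row should be read against the first: some overlap would arise without any correlation. The ordering of the three analyses is the same in every scenario. The power levels themselves are only as good as the assumptions.

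**The case against.** The strongest reply is that the text never says an episode is a score of 6 or more. That value defines active disease, which is a state. The Justification of 1C uses episodes as another word for flares, and its Safety item speaks of monitoring flares. A reader might infer that persisting activity is bound to be counted as an episode. The documents do not support that; they leave episode undefined. The point therefore holds conditionally, if activity is judged by the only threshold supplied.

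A reader might also infer that improvement cannot be seen at all. That goes too far. A fall from 10 to below 6 would show as inactive, and the tests for quantitative variables could be applied to a SLEDAI-2K score or its change. The plan does not exclude this; it simply does not say so.

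Nor is the comparison biased. Randomisation balances entry activity in expectation, and a valid two-group test already allows for chance imbalance. What is lost is precision and clear meaning, on a secondary outcome.

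Finally, the clinic rates in the 1A sample-size text (16% with active renal disease, 34% of juvenile patients active) should not be used for the share active at entry in 1C. The first is not a SLEDAI-2K threshold, the second is juvenile, and neither describes patients starting HCQ.

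What remains is that 1C states response and improvement as aims, sets no activity limit at entry, and names no analysis that uses the entry score. None of the replies removes this.

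**Conclusion.** The point stands as a recommended improvement to a secondary analysis. As written, 1C does not tie its objective of clinical response to any measure of change, and its named tests ignore the entry score. If the cut-off of 6 is what decides activity, the result mixes prior with new disease and misses falls that stay at 6 or above.

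The size cannot be fixed from the documents. For an assumed correlation of 0.4 to 0.7, adjustment removes 16% to 49% of the residual variance of the continuous score. In the illustrative scenarios, power was 18% to 37% with the cut-off and 63% to 75% with the adjusted score. Both results rest on assumed inputs. The primary outcome is unaffected, and there is no ground for calling the clinical comparison invalid.

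**What to change.** Amend STUDY DESIGN and STATISTICAL PLAN of 1C as follows.

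1. State that SLEDAI-2K is scored at the entry and month-6 visits. The three-monthly schedule stands in the design of 1A, and 1C refers to 1A only for methods, so the visits need naming here.
2. Define clinical response by the month-6 SLEDAI-2K, and compare arms with a linear model containing treatment arm and entry score. Report the adjusted difference with its confidence interval.
3. Report episodes separately, defined as new or worsening activity relative to entry. Fix in advance what counts as worsening, and include patients already at 6 or more. A rule that counts only moves from below 6 to 6 or more would discard a patient going from 10 to 20.
4. Tabulate results by active or inactive status at entry, as description.

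The cost is small: SLEDAI-2K recorded at two visits at which HCQ is already sampled, and slightly more analysis work. No extra patients and no change to treatment are needed.
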